The doses will be escalated until participants are on their full dose by 1 month. If a patient encounters intolerable side effects at full dose, then they will be able to remain on the highest dose regime that they can tolerate and this dose will be recorded. The total duration of the trial drug administration will be 1 year.

Note that no maximum time since the index lacunar ischaemic stroke will be set – patients will be eligible for the trial for several years after their lacunar stroke at the discretion of the local medical staff, as long as the index stroke was compatible with lacunar ischaemic stroke and competing pathologies as a cause of the stroke were excluded using contemporaneous MR imaging, or CT, as above. That is, that the index stroke was not a non-lacunar stroke, that it was ischaemic and not haemorrhagic, and that it was not a non-stroke based on clinical and MR imaging, or CT, acquired at the time of the stroke.

Note also that no minimum cut off cognitive score is set. The Montreal Cognitive Assessment (MOCA) will be collected at baseline but will not be an inclusion/exclusion criterion. The important point is that the patient has capacity to consent, in the opinion of the randomising doctor.

[figure not shown]
Throughout the trial, patients will continue to take their normal prescribed medication which will include stroke secondary prevention prescribed since their event as per national guidelines/usual post-stroke care in participating centres.

Four hundred patients will be recruited from UK stroke research network centres. The most active of these sites see 10-15 patients per month with suspected lacunar stroke, of whom 25-33% would be eligible. Some interested sites have indicated that they could randomise 1-2 per month. Patients will be recruited from hospital-based stroke services, including patients who have participated in previous completed studies and indicated that they would like to be informed of future stroke studies.

On entry to the study, participants will be assessed by the study researcher, including presenting history, past medical history, medication history, neurological examination, check of brain MR or CT scan, blood pressure measurement and cognitive testing. They will then be randomised.

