5.5 RANDOMISATION

5.5.1 Randomisation Procedures

The electronic randomisation system and trial database are hosted by the University of Nottingham. Randomisation involves minimisation on key prognostic factors including: age, sex, stroke severity (NIHSS), dependency resulting from the stroke, systolic blood pressure $\leq/ > 140$, smoker status, time after stroke, years of education. Years of education give an estimate of pre-morbid cognitive ability and predicts post-stroke cognitive impairment; BP and smoking predict recurrent stroke; delay since stroke reflects disease activity; age, sex and stroke severity are standard minimisation variables. This approach ensures concealment of allocation (note allocation concealment means that it is not possible to guess which treatment the next patient will be randomised to), minimises differences in key baseline prognostic variables, and improves statistical power. Randomisation will not be minimised by Centre because this may result in high rates of allocation prediction, but a pre-specified post-hoc analysis by centre will be performed to investigate and adjust for heterogeneity of treatment effect by centre.

Randomisation will allocate a trial treatment, which will be prepared by the local participating Pharmacy.

Note that randomisation will be performed during normal office hours (09.00 – 17.00) and the trial allows for randomisation to occur months or years after the stroke. Therefore, in the event of computer failure (for example: server failure), the investigator will wait until the computer system is re-established to perform the randomisation. Normally, this would only be a few minutes to two hours. However, if this delay requires the patient to return on a separate occasion to collect the drugs, then a separate appointment will be made and the patient's travel expenses covered as per other trial visits.

Patients will be randomised to one of the following at a 1:1 ratio as per Section 6.2:

- cilostazol versus no cilostazol
- isosorbide mononitrate versus no isosorbide mononitrate

resulting in a partial factorial comparison of cilostazol versus isosorbide mononitrate versus both drugs versus neither drug.

The randomisation algorithm will allocate a unique identifier which will be used to label the treatment pack containing the appropriate drug made up for the patient and dispensed by the local Pharmacy.

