7.2 STUDY ASSESSMENTS

Study assessments are shown in **Table 5** below, and in **Figure 2**.

Table 5: Study Assessments

Assessment	Prior to Baseline	Visit 1 Baseline	Week 1-2 FU	Week 3-4 FU	6 month FU	12 month FU
Screening for eligibility and Consent ¹ ;	X^s					
Confirm and document ongoing consent		X^s				
Medical including drug history		X^s				
Assess MR or CT diagnostic scan and send a copy to Edinburgh		X^s				
Randomisation		X^s				
Haematology (full blood count) and Biochemistry (urea, electrolytes, creatinine) – most recent value obtained since time of index stroke is acceptable unless clinical reason to expect change		X^s				
Blood Pressure recorded		X^s				X^{s,*}
Cognitive test: document years of education; Montreal Cognitive Assessment (MOCA)		X^s				
Timed Trail Making Test B		X^s				X^{s,*}
Dispense trial medication ²		X^s			X^s	
Structured questionnaire: symptoms; medication history and IMP tablet adherence			X^s	X^s	X^c	X^c
Structured Q: recurrent vascular events, mRS, TICS, TMOCA, SIS, ZUNG					X^c	X^c
Obtain IQCODE (post/phone) from relative						X^c
Follow-up brain MRI						X^s
Health Economics data: EQ-5D-5L, EQ-VAS						X^c
Adverse event / con meds reporting as necessary			X^s	X^s	X^{s,c}	X^{s,c}

¹Consent will be obtained before the data collection procedures commence or randomisation is performed.

Randomisation occurs at the end of the baseline visit. ^{*}at 12 months in some centres only. ²Dispensing in 3-monthly intervals is allowed. ^sAssessment performed by local site team. ^cAssessment performed by blinded assessor who is part of the central trial team.

SIS=Stroke Impact Scale, TICS= Telephone Interview for Cognitive Status, TMOCA= telephone MOCA.

Medical history: Will be performed by the study researcher and will include details of incident stroke, past medical history, vascular risk factors, medication history and years of education.

Baseline brain MR (preferred wherever possible) or CT: To identify the index stroke or exclude other causes of symptoms, and assess the burden of SVD – this is the clinical scan with T2, FLAIR, T1, T2* and diffusion imaging or CT obtained soon after the presentation with stroke that shows either:

- a recent, relevant (in time and location) acute lacunar infarct,

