8 DATA COLLECTION

Please see section 7.2 above for measurements and time points.

The medical history, cognitive assessment, and structured questionnaire for symptoms and adverse events will be obtained from the patient in person (and medical notes where necessary) and by telephone by the study researcher after appropriate training as required and entered into the electronic case record form. These researchers will also measure blood pressure, obtain blood samples for haematology and biochemistry as necessary (analysed in the hospital NHS haematology or biochemistry labs in the centre in which the patient has been recruited).

The researcher at each site will co-ordinate the appointment for one year MRI. A reminder that the MRI appointment is due will be sent by the Trial Co-ordinating Centre. The MRI will be performed in approved radiology departments using sequences specified for the trial.

All baseline medical, cognitive, scanning and laboratory data will be entered into a secure password protected electronic case record form (eCRF) run from the University of Nottingham, accessible to approved research staff for data entry. The data from central reading of MRI will be added to the eCRF data for statistical analysis. Participant and relative/carer contact details, required to perform Trial follow-up, will be stored in an encrypted secure password-protected database also provided by the University of Nottingham, separate to the Trial eCRF database, and only accessible to selected researchers in the Trials Unit, University of Edinburgh and the University of Nottingham.

Paper versions of the CRF (i.e. source data sheet) will be available to assist with data collection when interviewing patients at baseline and during follow-up visits in phone or in person. Paper CRFs will be filed in the patient's paper-based folder and held in a secure locked filing cabinet at site.

The MR or CT brain images obtained at diagnosis of the stroke and 1 year follow-up MRI will be anonymised and sent to Edinburgh where they will be assessed and quantified for the index stroke, features of small vessel disease and other features, using validated scores and volume measurements by an experienced rater. Images will only be identified by study ID.

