Composite outcome for phase III	MACE, dementia, non-vascular death, new MR signs	MACE, dementia, death	MACE, cognitive decline, dependency decline, all-cause death		MACE, cognitive impairment, dependency, all-cause death
1-beta (power)	80%	80%	80%	80%	80%
Event rate, control, pa	50%	10%	30%	30%	45%
Relative risk reduction	20%	20%	20%	30%	20%
Event rate, active, pa	40%	8%	24%	21%	36%
Total sample size	950	6626	1784	778	976
Total trial size, including losses	1250	7400	2000	900	1100

MACE: major adverse cardiac events; MRI: magnetic resonance imaging

12 Framework

The primary objectives are to assess the feasibility of recruitment and adherence to medication.

13 Statistical interim analyses and stopping guidance

13a Interim analyses: Data are tabulated twice annually prior to Trial Steering Committee (TSC) and Data Monitoring Committee (DMC) meetings. No unblinded comparative analyses will be performed until data collection has been completed and the database locked.

Prior to the final database lock, the database will be subject to a soft lock and the provisional data tabulated and analysed for review by the TSC and DMC. Any final queries will be raised and resolved prior to final database lock. Members of staff still involved in the collation of data and resolution of data queries will not attend the meeting and the data reviewed at the meeting will remain strictly confidential until the point of final database lock to avoid any bias.

13b Adjustments of significance level: There is no planned adjustment.

13c Stopping rules: There are no formal stopping rules, but the DMC have responsibility to make recommendations to pause or modify the study, should there be any safety or efficacy considerations.

14 Timing of final analyses

These will be performed once data collection has been completed and the database has been locked.

15 Timing of outcome assessments

Assessments will be performed at baseline, 1-2 weeks, 3-4 weeks, 6 and 12 months (**Table C**).

Table C. Assessments at baseline and follow-up by time point (adapted from protocol and ¹).

Assessment	Prior to Baseline	Visit 1 Baseline	Week 1-2	Week 3-4	Month 6	Month 12
Screening for eligibility and consent [†]	X ^s					
Confirm and document ongoing consent		X ^s				
Medical including drug history		X ^s				
Assess MR or CT diagnostic scan; send copy to Edinburgh		X ^s				
Randomisation		X ^s				

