- Recruitment of sufficient patients, i.e. 400 patients in 24 months in the UK (and taking account of interruption due to COVID-19).
- >95% of randomised patients are retained for follow-up at one year.

Secondary outcomes - participant

Tolerability: 75% of patients will be able to tolerate trial medication, in at least half dose, up to one year after randomisation (i.e. less than 25% will stop trial medication completely through inability to tolerate the drugs).

Safety

- Symptoms of systemic or intracranial bleeding.
- The absolute risk of death, including fatal haemorrhage, does not differ significantly, i.e. fall outside the upper 95% CI of 2% per year on trial drugs versus no trial drugs, when given in addition to guideline stroke prevention drugs.
- There are no new ischaemic or haemorrhagic brain lesions or increase in SVD lesions on one year MRI significantly (at the p<0.01 level).

Efficacy

- Individual event-rates for stroke, TIA, myocardial ischaemia, cognitive impairment and dementia.
- The *combined rate* of recurrent stroke, MI, death, mild cognitive impairment (including dementia), dependency and new stroke lesions on scanning at 1 year will be 40-50% at one year after enrolment in order to allow detection of a modest but clinically-important reduction in poor outcomes in a phase III trial.
- Health economic measures include the health utility score (EQ-5D-5L) and the visual analogue score (EQVAS) at 12 months.

26b Units: Units will be shown in tables.

26c Calculations/transformations: Quality of life using UK weightings.

Brain frailty

Based on neuroimaging:

- Brain frailty = Atrophy + WML + Previous stroke lesion ⁷

- SVD score for CT = WML, lacunes; for MRI includes WMH, lacunes, PVS and microbleeds ¹⁵

Montreal cognitive assessment-modified (MoCA-m) trails

Since Trails A and B are performed, the MoCA trail is not collected but rather estimated from the Trails B score:

- If Trails B score <12 then MoCA trail = 0
- If Trails B score >=12 then MoCA trail = 1

27 Analysis methods

27a Methods

Primary endpoint

- Tabulation and graphical presentation of participant recruitment aiming for 400 participants in 24 months.
- Tabulation of retention of participants at one year aiming for >95%.

Analyses of secondary outcomes

Tabulations of:

- Tolerability to trial medications aiming for 75% of patients taking at least half dose for up to one year after randomisation.

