Change from baseline	XX	XX [XX, XX]	XX [XX, XX]	XX [XX, XX]	OLR	XX	XX [XX, XX]	XX [XX, XX]	OLR	XX	XX [XX, XX]	XX [XX, XX]	OLR	XX
WMH change from randomisation	XX	XX (X)	XX (X)	XX (X)	BLR	XX	XX (X)	XX (X)	BLR	XX	XX (X)	XX (X)	BLR	XX
Frontal (%)					OLR	XX			OLR	XX			OLR	XX
More	XX	XX (X)	XX (X)	XX (X)			XX (X)	XX (X)			XX (X)	XX (X)		
Less	XX	XX (X)	XX (X)	XX (X)			XX (X)	XX (X)			XX (X)	XX (X)		
No Change	XX	XX (X)	XX (X)	XX (X)			XX (X)	XX (X)			XX (X)	XX (X)		
Parietal (%)					OLR	XX			OLR	XX			OLR	XX
More	XX	XX (X)	XX (X)	XX (X)			XX (X)	XX (X)			XX (X)	XX (X)		
Less	XX	XX (X)	XX (X)	XX (X)			XX (X)	XX (X)			XX (X)	XX (X)		
No Change	XX	XX (X)	XX (X)	XX (X)			XX (X)	XX (X)			XX (X)	XX (X)		
Occipital (%)					OLR	XX			OLR	XX			OLR	XX
More	XX	XX (X)	XX (X)	XX (X)			XX (X)	XX (X)			XX (X)	XX (X)		
Less	XX	XX (X)	XX (X)	XX (X)			XX (X)	XX (X)			XX (X)	XX (X)		
No Change	XX	XX (X)	XX (X)	XX (X)			XX (X)	XX (X)			XX (X)	XX (X)		
Basal ganglia (%)					OLR	XX			OLR	XX			OLR	XX
More	XX	XX (X)	XX (X)	XX (X)			XX (X)	XX (X)			XX (X)	XX (X)		
Less	XX	XX (X)	XX (X)	XX (X)			XX (X)	XX (X)			XX (X)	XX (X)		
No Change	XX	XX (X)	XX (X)	XX (X)			XX (X)	XX (X)			XX (X)	XX (X)		
Posterior fossa (%)					OLR	XX			OLR	XX			OLR	XX
More	XX	XX (X)	XX (X)	XX (X)			XX (X)	XX (X)			XX (X)	XX (X)		
Less	XX	XX (X)	XX (X)	XX (X)			XX (X)	XX (X)			XX (X)	XX (X)		
No Change	XX	XX (X)	XX (X)	XX (X)			XX (X)	XX (X)			XX (X)	XX (X)		
Old vascular lesions (%)														
Old vascular lesions	XX	XX (X)	XX (X)	XX (X)	BLR	XX	XX (X)	XX (X)	BLR	XX	XX (X)	XX (X)	BLR	XX
Old cortical infarct	XX	XX (X)	XX (X)	XX (X)	BLR	XX	XX (X)	XX (X)	BLR	XX	XX (X)	XX (X)	BLR	XX
Old striatocapsular infarct	XX	XX (X)	XX (X)	XX (X)	BLR	XX	XX (X)	XX (X)	BLR	XX	XX (X)	XX (X)	BLR	XX

	N	All	OR/MD/ p- value				OR/MD/ p- value				ISMN + Cil		OR/MD/ p- value	
			ISMN	No ISMN	(95%CI)	HR	Cil	No Cil	(95%CI)	HR	None	(95%CI)	HR	p-value
Old borderzone infarct	XX	XX (X)	XX (X)	XX (X)	BLR	XX	XX (X)	XX (X)	BLR	XX	XX (X)	XX (X)	BLR	XX
Old lacunar infarct	XX	XX (X)	XX (X)	XX (X)	BLR	XX	XX (X)	XX (X)	BLR	XX	XX (X)	XX (X)	BLR	XX
Number of lacunes (%)				OLR	XX			OLR	XX			OLR	XX	
1	XX	XX (X)	XX (X)	XX (X)			XX (X)	XX (X)			XX (X)	XX (X)		
2	XX	XX (X)	XX (X)	XX (X)			XX (X)	XX (X)			XX (X)	XX (X)		
3	XX	XX (X)	XX (X)	XX (X)			XX (X)	XX (X)			XX (X)	XX (X)		
4	XX	XX (X)	XX (X)	XX (X)			XX (X)	XX (X)			XX (X)	XX (X)		
>=5	XX	XX (X)	XX (X)	XX (X)			XX (X)	XX (X)			XX (X)	XX (X)		

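### New-lesion and WMH-change outcomes are measured from a diagnostic scan that may pre-date randomisation by months or years, so imaging rates are not one-year-from-enrolment rates

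*SAP*

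**What the plan says.** **Which scans exist.** Protocol 7.2 describes the baseline image: "this is the clinical scan with T2, FLAIR, T1, T2* and diffusion imaging or CT obtained soon after the presentation with stroke". Protocol 8 names two time points for central reading: "The MR or CT brain images obtained at diagnosis of the stroke and 1 year follow-up MRI will be anonymised and sent to Edinburgh". In the SAP schedule (Table C) the baseline imaging step is "Assess MR or CT diagnostic scan; send copy to Edinburgh"; the only study MRI is at month 12.

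**How old the first scan may be.** Protocol 3 states: "Note that no maximum time since the index lacunar ischaemic stroke will be set", and adds that "patients will be eligible for the trial for several years after their lacunar stroke". Protocol 5.5.1 repeats that "the trial allows for randomisation to occur months or years after the stroke". The SAP expects a wide spread: Table 1 splits onset-to-randomisation at 100 days, and the Figure 2 subgroups include 365 days or more.

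**What is compared.** SAP 27a takes new infarcts and haemorrhages, and change in WMH, microhaemorrhages, lacunes and atrophy, from the central reads of baseline imaging and the one-year MRI. One Table 9 row is nevertheless labelled "WMH change from randomisation".

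**Where the lesions are used.** SAP 26a counts imaging lesions in its combined rate: "new stroke lesions on scanning at 1 year will be 40-50% at one year after enrolment". The 26a safety criterion asks for no significant increase in MRI lesions at p<0.01. SAP 11b describes a phase III composite that includes new MRI signs. SAP Section 7 says the next trial's primary outcome will likely include them and that their rates will be assessed here.

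**The concern.** A lesion that is absent on the diagnostic scan and present on the one-year MRI may have arisen before the patient entered the trial. The plan has no scan at randomisation, no limit on the age of the diagnostic scan, no rule for dating a lesion to before or after randomisation, and no scaling of change by the interval between scans.

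Two things are at stake. The first is absolute rates, which are a main product of this trial: an imaging rate presented as occurring within a year of enrolment would be too high for late entrants. The second is the size of any treatment effect on imaging. Treatment can act only on the part of the interval after randomisation, so an effect on that part is spread over a longer window. That matters for the MRI safety criterion, where an odds ratio nearer 1 makes it easier to find no significant increase.

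**Working it through.** **The plan's own figure.** The point disputes no computed figure; the nearest is the phase III size. For 45% against 36%, two-sided 5%, 80% power:

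- n per arm = [1.960·√(2·0.405·0.595) + 0.842·√(0.45·0.55 + 0.36·0.64)]² / 0.09² = 465.8.
- With the Fleiss correction, (465.8/4)·[1 + √(1 + 4/(465.8·0.09))]² = 487.8, so 488 per arm and 976 in total, as stated in SAP Table B, model D.
- 976/0.90 = 1,084.4, that is 1,085, against a stated 1,100.

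The arithmetic reproduces. The question is what the event rate fed into it represents.

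**Inputs for the illustration.**

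- Time on treatment: 1 year (Protocol 3).
- Relative reduction: 20%, the planning value in SAP 11b.
- T, the years from diagnostic scan to randomisation: not in the documents, so varied.
- r, the annual probability of a new lesion: not in the documents. 10% is assumed, with a range of 5% to 20%.
- Accrual is taken as constant, and treatment as acting only in the final year.

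**Formulas.**

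- Pre-treatment share of the scan interval = T/(T+1).
- Recorded proportion in controls = 1 − (1−r)^(T+1).
- Recorded proportion on treatment = 1 − (1−r)^T·(1−0.8r).

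| T (years) | Pre-treatment share | Controls, r=5% | r=10% | r=20% | Apparent relative reduction, r=10% |
|---|---|---|---|---|---|
| 0 | 0% | 5.0% | 10.0% | 20.0% | 20.0% |
| 0.27 (100 days) | 21.5% | 6.3% | 12.6% | 24.7% | 15.5% |
| 0.5 | 33.3% | 7.4% | 14.6% | 28.4% | 13.0% |
| 1 | 50.0% | 9.8% | 19.0% | 36.0% | 9.5% |
| 2 | 66.7% | 14.3% | 27.1% | 48.8% | 6.0% |
| 3 | 75.0% | 18.5% | 34.4% | 59.0% | 4.2% |

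Worked case, T=1 and r=10%: controls 1 − 0.9² = 19.0%; treated 1 − 0.9·0.92 = 17.2%.

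**Effect scale, same case.**

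- Odds ratio within the treated year: (0.08/0.92)/(0.10/0.90) = 0.78.
- Odds ratio as recorded: (0.172/0.828)/(0.19/0.81) = 0.89.
- The risk difference barely moves: 2.0 points within the treated year, 1.8 points as recorded.

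Attenuation is therefore mainly a feature of relative measures, and Table 9 plans logistic models, binary and ordinal, for nearly all its lesion and change rows. Adjusting for time after stroke accounts for its association with the outcome. It does not turn the whole-window odds ratio into one for the year on trial.

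**The case against.** The strongest reply is that the reach is limited, and much of that stands.

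- **The 40-50% target.** A reader might infer that this criterion is inflated wherever it appears. The documents do not support that. Protocol 2.2.2, the SAP 27a tabulation, 27f, Table 2 and Figure 2 all leave imaging out, and the 27a comparison specifies clinically evident stroke. Only 26a adds scan-detected lesions, so the inflation is confined to that definition.
- **Table 9 labels.** A reader might infer that the whole table is mislabelled. Only one row refers to randomisation; the other change rows are headed as change from baseline, which fits the definition in Protocol 7.2.
- **Bias between arms.** A reader might infer that the treatment comparisons are biased. Change before randomisation is balanced in expectation, and time after stroke is both a minimisation factor and a continuous covariate (SAP 10, 27b). What remains is attenuation of odds ratios.
- **Phase III size.** A reader might infer that 1,100 is too small for this reason. That does not follow. SAP 11b's text pairs the MRI-sign composite with 45%, but in Table B the 45% row is model D, which has no imaging, and Protocol 9.1 gives reasons against an MRI-based outcome. The link to phase III rests on the 11b text and on Section 7's intention to use new MRI signs.
- **Size.** Neither the interval distribution nor the lesion rate is in the documents. The 100-day split in Table 1 suggests that many entrants may be early, and they are little affected.

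None of this makes the label correct for late entrants or turns the recorded lesion proportion into a one-year rate. Randomisation and covariate adjustment do not correct an absolute rate.

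**Conclusion.** The point holds for imaging outcomes only. The WMH row and the new-infarct and new-haemorrhage outcomes run from the diagnostic scan, not from randomisation. The imaging component of the 26a combined rate, and any new-MRI-sign rate carried into phase III planning, would be overstated as one-year rates. Imaging odds ratios, including those behind the p<0.01 safety criterion, move towards 1. Clinical event rates and the primary endpoint of recruitment and retention are not affected.

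The size is conditional. With an assumed annual rate of 10% (5-20%), a scan one year before randomisation gives about 19% (10-36%), and a true 20% relative reduction appears as 9-10%. At 100 days the recorded rate is 12.6% (6.3-24.7%). These figures assume constant accrual and a single value of T. If lesions accrue faster soon after a stroke, the pre-treatment share would be larger than shown.

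**What to change.** 1. Relabel the one Table 9 row as change from diagnostic scan.
2. Report the distribution of the scan-to-randomisation and scan-to-scan intervals, overall and by arm. Table 1 already lists onset-to-randomisation and stroke-to-scan days, whose difference gives the first. State the origin of the time-to-scan rows in Tables 5 and 9, which is undefined.
3. Wherever new lesions serve as an event rate (the 26a combined rate, phase III planning), report them per year of scan interval. Show the 26a rate with and without the imaging component, and say which composite is judged against 40-50%.
4. Add a sensitivity analysis of the imaging outcomes limited to patients whose diagnostic scan fell within a short time of randomisation, with the cut-off fixed in advance.

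A separate scan-interval covariate is optional. The diagnostic scan is done soon after the stroke, so the interval is close to time after stroke plus one year, and time after stroke is already in the models. What it would add is mostly the timing of the follow-up scan, which is a post-randomisation variable.

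The cost is SAP wording and a few extra table lines from dates already collected. The downsides are a lower reported imaging rate and a smaller, less precise sensitivity set.
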